4.0 Study Design and Randomization

4.1 Study Design and Randomization (P1, EHR-based antibiotic decision support)

Effectiveness of the EHR-based antibiotic decision support application for promoting guideline-concordant antibiotic prescribing in children presenting for emergency care will be evaluated in a pragmatic, cluster randomized crossover study conducted over a period of 18 months that includes two respiratory seasons. Our institutions possess demonstrated experience in the execution of these pragmatic designs.¹⁷⁻²¹ Crossover will occur each month in a randomly determined sequence within each hospital. To ensure balanced representation of each arm in periods of both low and high pneumonia prevalence, randomization will occur in 3 permuted blocks (size=6). The cluster-randomized crossover design also improves efficiency and reduces potential problems related to cluster imbalance when using a small number of clusters.⁶⁷ The antibiotic decision support application will be provided to those randomized to the intervention arm, whereas the control arm will receive usual care. Due to the nature of the intervention, blinding of treating providers will not be possible. Importantly, since this is a trial focused on provider behavior, all children will receive standard of care management. All treatment decisions will be made by the clinical providers and will not be restricted or altered in any way.

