8.0 Statistical Considerations

8.1 Power and Sample Size (P1)

Based on ED and hospitalization data from our hospitals during the conduct of the EPIC study, we anticipate nearly 2000 total children with pneumonia will be evaluated annually during the conduct of these studies. Assuming conservatively that data for 750 children are enrolled in each arm, and 30% guideline-concordant antibiotic use in the usual care arm (based on our prior study of antibiotic use in the EPIC cohort)²³, we will be able to detect an absolute difference of $\geq 6.8\%$ in guideline-concordant prescribing at an alpha level of 0.05 with 80% power. Effective sample size may be reduced due to the cluster randomized nature of the study (a conservative estimate for effective sample size would be around 500 children in each arm).

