An important consideration in our analysis is the possibility of contamination effects in the usual care arm related to changes in provider behavior due to past exposures and awareness of the intervention. Such contamination would be expected to bias toward the null hypothesis. We posit that such effects will be of minor concern since 1) guideline-concordant prescribing at our institutions remains low despite the presence of both national and local practice guidelines and order sets for several years; 2) the ED is a busy environment with many providers (e.g., 40+ ED faculty plus mid-level providers and fellows/residents at Vanderbilt alone), such that repeated exposure to the intervention by any one provider would be infrequent, particularly early during the study period and during times of low pneumonia prevalence; and 3) resident physicians, the providers responsible for the majority of order entry and thus directly exposed to the intervention, rotate on a monthly schedule and only work in the ED once each year. We have designed our randomization and monthly crossover periods around these important considerations. Nevertheless, we acknowledge the potential for contamination, and we will formally evaluate for such effects in a secondary analysis by modeling the monthly proportions of guideline-concordant prescribing in each arm over the duration of the study period. We will then compare prescribing trends in both arms with a historical trend estimated from monthly proportions of guideline-concordant prescribing in the year prior to study initiation. By comparing prescribing trends in each arm to this historical trend, we will estimate both the degree of potential contamination as well as the independent impact of the intervention.

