8.3 Potential Limitations and Alternative Approaches (P1)

We do not anticipate major difficulties designing or implementing our antibiotic decision support application. If challenges arise, our experienced team possesses the necessary expertise, past experience, and institutional resources to address and overcome them. Design challenges will be addressed by our usability and decision support experts to troubleshoot and develop effective solutions prior to and following implementation. Alternative analytic approaches were considered, including quasi-experimental step wedge designs and randomization at the provider or patient level. The cluster randomized monthly crossover design was selected since it is less subject to temporal bias (compared to the step wedge approach) and minimizes problems with contamination in the usual care arm (compared to provider or patient-level randomization) as outlined above. In addition to the analyses outlined above, if we fail to demonstrate meaningful outcome differences between the two arms, we will conduct exploratory analyses to elucidate reasons for lack of intervention effectiveness.

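### As specified, the Phase 1 contamination analysis cannot tell carry-over from any other departure from the pre-study trend

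*Protocol*

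**What the plan says.** Protocol 4.1 sets the schedule: "Crossover will occur each month in a randomly determined sequence within each hospital", in three permuted blocks of six over 18 months. No washout is described.

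Protocol 8.2 raises contamination of the usual-care arm, accepts that it would pull the result toward the null, and argues that it will be minor, partly because "repeated exposure to the intervention by any one provider would be infrequent". It then commits to a secondary analysis in two steps. The first models monthly concordance in each arm across the trial. The second compares both arms' trends with a trend fitted to the year before the trial. From this, it says, "we will estimate both the degree of potential contamination as well as the independent impact of the intervention". It gives no model form, season term, or cohort definition for the historical year.

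Protocol 8.3 prefers the crossover design because "it is less subject to temporal bias (compared to the step wedge approach"). It also promises unspecified exploratory analyses if no meaningful difference is found.

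SAP 10.1 treats enrolment month as a random effect. SAP 10.1 to 10.3 contain no contamination analysis, no term for the previous period's arm and no arm-by-time term.

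**The concern.** The historical comparison identifies contamination and tool impact only if the old trend would have continued unchanged, and the plan never states that assumption. A new secular shift, a season effect, or the diagnosis-confirmation alert that the trial places in both arms (Protocol 6.1) could each move concordance away from the old trend. In the control arm that movement would be read as contamination. In the intervention arm it would be added to the tool's impact.

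The first step, modelling monthly proportions in each arm, could help, because a shift common to both arms leaves the gap between them roughly unchanged while accumulating contamination narrows it. But the protocol states no arm-to-arm comparison over time and no carry-over contrast. If the observed difference is small, the analysis as written cannot say how much of that is due to carry-over.

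**Working it through.** **1. The plan's own figure.** Inputs from Protocol 8.1: "Assuming conservatively that data for 750 children are enrolled in each arm"; "30% guideline-concordant antibiotic use in the usual care arm"; and a detectable difference of 6.8 points "in guideline-concordant prescribing at an alpha level of 0.05 with 80% power". The pooled two-proportion formula, two-sided, gives 6.82 points (power 79.8% at 6.8), so the figure reproduces. At the protocol's effective size of about 500 per arm, the detectable difference is 8.4 points and power at 6.8 points is 62.6%.

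**2. What contamination would cost.** Suppose a share f of a 6.8-point effect leaks to controls (f is assumed; the documents give none). The observed difference is 6.8 × (1 − f).

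| f | Difference (points) | Power, 750 per arm | Power, 500 per arm |
|---|---|---|---|
| 10% | 6.1 | 71% | 54% |
| 25% | 5.1 | 55% | 40% |
| 50% | 3.4 | 28% | 20% |

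**3. Two situations, one data set.** Let the historical trend be flat at 30.0%, and read each arm's departure from it as Protocol 8.2 implies.

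- A: true effect 6.8, half leaks, no departure from trend. Control = 30.0 + 3.4 = 33.4%; intervention = 30.0 + 6.8 = 36.8%.
- B: true effect 3.4, no leakage, a 3.4-point departure in both arms. Control = 30.0 + 3.4 = 33.4%; intervention = 30.0 + 3.4 + 3.4 = 36.8%.

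In both, the method reports contamination of 3.4 and impact of 6.8. In B the contamination is zero and the impact is doubled.

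**4. Season.** An intercept, a linear trend and 11 calendar-month indicators make 13 columns on 12 monthly points (rank 12), so trend and free season effects cannot both be fitted. If season is ignored, an assumed cosine of amplitude 3 points can move a straight-line projection at mid-trial by up to about 7.3 points either way.

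**5. Precision of a straight-line projection.** Number the historical months 1 to 12, so mid-trial is t = 21.5 and the end is t = 30. With n children per month, SE = √[(0.30 × 0.70 / n) × (1/12 + (t − 6.5)²/143)].

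- 2000 children in the year (n ≈ 167): SE 4.57 at mid-trial, 95% half-width 9.0 points; 13.8 at the end.
- 1000 children (n ≈ 83): SE 6.46, half-width 12.7 points; 19.5 at the end.

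These use binomial error only.

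**6. What the randomised sequence allows.** Assume three intervention and three control periods per block. Per hospital, the expected number of control periods that follow an intervention period is 3 blocks × 5 pairs × (1/2 × 3/5) + 2 block joins × 1/4 = 4.5 + 0.5 = 5.0. The number that follow a control period is 3 × 5 × (1/2 × 2/5) + 2 × 1/4 = 3.0 + 0.5 = 3.5. The remaining 0.5 is a first period. Over two hospitals that is 10 against 7 hospital-months.

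With 1500/36 = 41.7 children per hospital-month, this is 417 against 292 children. SE = √[0.21 × (1/417 + 1/292)] = 3.5 points, half-width 6.9; averaged over simulated sequences it is 7.0. An assumed between-month SD of 2 to 4 points raises it to 7.3 to 8.0. With 3000 children (2000 per year × 1.5 years) it is about 4.8 before clustering.

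**7. Arm-by-time term.** Scale time from first to last month to length 1 (variance 0.0931) and take residual variance 0.33 × 0.67/41.7 = 0.0053. Then SE ≈ √[0.0053 / (36 × 1/4 × 0.0931)] ≈ 8.0 points. The half-width for the change in the gap is about 16 points.

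**The case against.** The protocol deserves credit on several points, and stronger readings should be resisted.

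- **Primary result.** A reader might infer that the historical step brings temporal bias back into the trial's main result. It does not. The primary contrast in Protocol 8.2 and SAP 10.1 uses concurrent, block-randomised control periods and no historical data.
- **Only check.** A reader might infer that history is the sole safeguard. Modelling within the trial is also planned; what is missing is a stated contrast between arms.
- **Any secular rise.** The comparator is a trend. A rise already present in the historical year would be carried forward; only a departure from it would be misread.
- **Exposure counts.** About 92% of control periods come after first tool use ((9 − 0.75)/9 per hospital, since 3/4 of a control period is expected before it). That describes the calendar, not the ordering clinicians. Dividing 750 exposed children by 2 hospitals and 40 faculty gives 9.4 each over nine intervention months, about one a month. It also leaves out the other providers, and the residents who place most orders and rotate monthly. The documents do not support calling the protocol's claim of infrequent exposure contradicted.
- **An uninterpretable null.** Usage statistics, recorded reasons for discrepant prescribing and the promised exploratory analyses all bear on whether the tool failed.
- **Straight-line projection.** The protocol does not specify one. The prior year covers each calendar month once, so month-matching is possible. That handles a stable season but leaves a departure from trend just as ambiguous.

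All of this stands. None of it makes the claim to estimate both quantities from the historical comparison correct.

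**Conclusion.** The concern holds for the secondary contamination analysis. As specified, it cannot separate contamination from any other departure from the pre-study trend, and it can return a wrong answer for both quantities that it claims to estimate (step 3). A linear historical projection would also be less precise, at about 9 to 13 points at mid-trial, than the 6.8 points the trial is designed to detect. The within-trial contrast that the randomisation already permits is somewhat tighter, at about 7 to 8 points. The limit lies in the written analysis, not the design.

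This rests on assumptions that the documents do not settle: three and three periods per block, equal monthly volumes, 1000 to 2000 historical children, and the chosen leakage shares, seasonal amplitude and between-month SD. The non-identification argument needs none of them. The correction is worth making before analysis, but it does not threaten the primary comparison.

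**What to change.** In Protocol 8.2 and SAP 10.1, move the contamination analysis inside the trial:

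- **(a)** Add a previous-period-arm term that compares control periods after intervention with control periods after control, leaving out each hospital's first period.
- **(b)** Add an arm-by-time term for accumulating contamination.

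Report both with 95% confidence intervals as sensitivity analyses. Keep the historical trend as description only and define its cohort: Protocol 7.3 triggers data collection from the pneumonia alert and names no source for the pre-study year. Delete the claim that the comparison estimates the tool's independent impact. If provider identity is retained (it is not among the data listed in Protocol 7.3 or SAP 7.1), a count of each provider's earlier tool displays may be added. That analysis is observational and should be labelled exploratory.

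The cost is wording and two model terms, with no new data for (a) or (b). The downside is precision. Term (a) sees mainly short-term carry-over and (b) would miss immediate, constant carry-over. At the half-widths above, neither can exclude modest contamination, and the SAP should say so.

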8.3 Potential Limitations and Alternative Approaches (P1)

We do not anticipate major difficulties designing or implementing our antibiotic decision support application. If challenges arise, our experienced team possesses the necessary expertise, past experience, and institutional resources to address and overcome them. Design challenges will be addressed by our usability and decision support experts to troubleshoot and develop effective solutions prior to and following implementation. Alternative analytic approaches were considered, including quasi-experimental step wedge designs and randomization at the provider or patient level. The cluster randomized monthly crossover design was selected since it is less subject to temporal bias (compared to the step wedge approach) and minimizes problems with contamination in the usual care arm (compared to provider or patient-level randomization) as outlined above. In addition to the analyses outlined above, if we fail to demonstrate meaningful outcome differences between the two arms, we will conduct exploratory analyses to elucidate reasons for lack of intervention effectiveness.

8.4 Power and Sample Size (P2)

As outlined in P1, we anticipate nearly 2000 children with pneumonia will be evaluated annually during the conduct of these studies. Assuming conservatively that data for 2000 children (1000 in each arm) are captured during the two-year study period, and 90% appropriate site of care disposition in the usual care arm (based on data from the EPIC cohort)²³, we will be able to detect an absolute difference of $\geq 3.4\%$ in appropriate care disposition at an alpha level of 0.05 with 80% power.

8.5 Analysis (P2)

Logistic regression models will be performed to compare appropriate site of care disposition between the two study arms, controlling for important baseline covariates (e.g., age, season, provider type) to maximize power. Robust standard errors will be calculated to account for hospital clustering effects. We will also perform analyses to assess for interactions between two study arms and predicted risk for severe outcomes, age, provider type, and initial site of care, to identify subgroups in whom decision support may be most useful. Similar analyses will be conducted for the proposed secondary and exploratory outcomes along with cox regression model for hospital length of stay outcome.

8.6 Potential Limitations and Alternative Approaches (P2)

In contrast to our studies of antibiotic decision support, we chose to randomize at the individual level rather than monthly crossovers since potential for contamination effects is minimal (i.e. risk estimates are unique to each individual's set of circumstances and linked to a complex algebraic equation). Although we hypothesize that supplying providers with objective prognostic information will improve care decisions, this information could lead to unintended outcomes, such as increased hospitalizations in low risk children. This would be an important finding in itself, as it contrasts with prior studies in adults highlighting the usefulness of adult pneumonia severity tools, and provides valuable data regarding how risk information is interpreted and applied.

9.0 Risks to Participants

All study subjects will receive standard of care. All decisions regarding management, including antibiotic use and site of care disposition, will be at the discretion of the treating provider and will not be restricted or altered in any way by the study. This study does not involve an investigational intervention given or

administered directly to patients (i.e. no treatment assignments will be made). Therefore, this study poses no greater than minimal risk to study participants. Vanderbilt is at the forefront of these pragmatic, minimal risk clinical trial designs, and our study team benefits greatly from the experiences and expertise of our colleagues who have completed similar studies under waiver of informed consent. The potential benefit of this study would come through more effective therapy.

The study coordinator, with PI oversight, is responsible for ensuring protocol compliance, data integrity, and participant safety. This protocol presents minimal risks to participants and adverse events or other problems are not anticipated. In the unlikely event that such events occur, unanticipated problems involving risks to subjects or others will be reported immediately to the PI and responsible IRBs, and in writing within 5 days to the IRB and any appropriate funding and regulatory agencies. The PI will apprise fellow investigators and study personnel of all adverse events that occur during the conduct of this research project through regular study meetings. Annual reports will be submitted to the responsible IRBs summarizing study progress, adverse events, complaints about the research or withdrawals, and any protocol violations.

Although the study poses no greater than minimal risk to human subjects, we have appointed an independent data and safety monitoring board (DSMB) due to the inclusion of children and the multi-center nature of the study. The DSMB is comprised of three individuals with expertise relevant to the study, including biostatistics, and prior experience serving in this capacity. The DSMB will be independent of the study team and will conduct formal data and safety evaluations at least every six months. During these meetings, the DSMB will assess study progress, including subject accrual and retention, data quality, and subject safety in a confidential manner. The DSMB will make recommendations regarding whether the study should continue unchanged or require modification/amendment. Based on the findings of the data and safety monitor's reports, the PI, associated IRBs, and any other appropriate funding or regulatory agencies have the authority to stop or suspend the study or require modifications.

10.0 Privacy/Confidentiality Issues

Privacy and confidentiality is of the highest priority, and all efforts will be made to keep personal information and research records private throughout these studies. Records and documents pertaining to the conduct of this study will be kept in HIPPA-compliant, secure, password protected databases or in locked files accessible only by a limited number of study personnel. All patient data will be coded using a unique study ID. No PHI will be shared outside of the key study personnel at each institution and no PHI will be shared between institutions. The information from the research study may be published using aggregate results; however, no individual subject will be identified.

11.0 Reporting of Adverse Events or Unanticipated Problems involving Risk to Participants

The PI is responsible for monitoring the data, assuring protocol compliance, and conducting safety reviews. Adverse events or other problems are not anticipated. In the unlikely event that such events occur, unanticipated problems involving risks to subjects or others will be reported immediately to the PI and responsible IRBs, and in writing within 5 days to the IRB and any appropriate funding and regulatory

agencies. The PI will apprise fellow investigators and study personnel of all adverse events that occur during the conduct of this research project through regular study meetings. Annual reports will be submitted to the responsible IRBs summarizing study progress, adverse events, complaints about the research or withdrawals, and any protocol violations.

12.0 Study Withdrawal/Discontinuation

The investigators may choose to withdraw a subject if it is judged to be in the participant's best interest, or if the subject no longer meets eligibility criteria (see Section 5.0). Due to the observational nature of the study, there are no formal interim analyses or planned halting criteria.

13.0 Follow-Up and Record Retention

The anticipated study duration is 24 months for P1 and 24 months for P2. As this study does not include direct contact with enrolled subjects, there is no anticipated follow up. Records will be maintained in accordance with IRB, institutional, and sponsor policies.

## 1 INTRODUCTION

This document describes the statistical procedures that will be utilized for the ICE-CAP protocol. This statistical analysis plan (SAP) describes the methods of statistical analysis. The initial draft SAP (Version 0.1) was written prior to any data being analyzed in order to avoid bias. Any subsequent changes that occur to the study protocol warranting changes to the analysis procedures will be documented in the SAP. Table 1 below will be used for tracking changes to the SAP.

Table 1. Statistical Analysis Plan Versions

Version	Date of Approval	Major Changes from Prior Version
1.0	Jul 30, 2018	-
1.1	Feb 1, 2020	Update study site; clarification for concordance definitions; minor edits for clarity

## 2 PROTOCOL OBJECTIVES FOR PHASE 1

### 2.1 Primary

- a) PO 1: To compare proportions of participants exclusively receiving guideline-concordant antibiotic therapy during the first 24 hours of care with or without EHR-based decision support in children 0.5-17 years of age presenting for emergency care.

